8.3 Reporting of Serious Adverse Events and Unanticipated Problems

When an adverse event has been identified, the study team will take appropriated action necessary to protect the study participant and then complete the Study Adverse Event Worksheet and/or log. The sponsor-investigator will evaluate the event and determine the necessary follow-up and reporting required.

8.3.1 Sponsor-Investigator reporting: notifying the Mayo IRB

The sponsor-investigator will report to the Mayo IRB any UPIRTSOs and Non-UPIRTSOs according to the Mayo IRB Policy and Procedures.

8.4 Stopping Rules

Study enrollment and treatment procedures will be suspended in the event that 3 successive subjects experience a Serious Adverse Event within the first 3 months after treatment. The study would only be resumed after a thorough review of the incidents and any corrective and preventative actions have been put in place along with consultation between the study team and the IRB.

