1.4 Dose Rationale and Risk/Benefits

We will dose PRP in a manner similar to previous trials. (Gentile, Trink, Cerveli) Fresh PRP will be harvested from the individual and their own PRP administered at three time points, once every 4 weeks for a totally treatment time of 12 weeks. Minoxidil will be used according to FDA and manufacturer instructions daily for 12 weeks.

Risks associated with PRP therapy include possible pain, redness, and/or irritation at the site of injections for up to 2-3 days post injection. Published human data indicate no significant adverse events related to injection of PRP into the skin and previous authors utilizing similar protocols reported no infection, fever, hematoma, tissue hypertrophy, or major adverse events among the subjects. (Singhal) (Cerveli) (Gentile) (Trink) (Gkini) Known possible risks for Minoxidil include chest pain, rapid heartbeat, faintness, dizziness, sudden or unexplained weight gain, swelling of the hands or feet, scalp irritation or redness, changes in hair color and texture, and unwanted facial hair growth.

[figure not shown]
2 Study Objectives

The overall goal of this study is to develop regenerative cell therapy for use in female patients with AGA. The primary objective of this proposal is to conduct a pilot study on the efficacy of using PRP to treat this type of hair loss in females.

3 Study Design

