5.2 Treatment Regimen

Patients will be randomized into a PRP then MNX (Arm A) or MNX then PRP group (Arm B). Patients randomized to Arm A will receive injections of PRP using the nappage technique (Sivagnanam) every 4 weeks for a total of 3 treatments over 12 weeks. Patients will then have a 2 month (8 week) washout period lasting until the end of month 4. Starting on month 5 they will receive crossover treatment with Minoxidil by applying the 5% foam once daily following manufacture instructions (Rogaine For Women) for a total of 3 months after which they will be followed until 1 year after enrollment. Patients randomized to Arm B will apply Minoxidil topical foam once daily following manufacture instructions for a total of 3 months followed by a two month (8 week) washout period. At the 5 month mark, the patients in Arm B will receive crossover treatment with PRP harvested and administered in the same manner as the patients in Arm A. At the end of the PRP treatment patients in Arm B will be followed until 1 year after enrollment.

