6.1 PRP vs Minoxidil Study Calendars

Arm A – PRP then MNX

Procedure	Baseline	Week 1	Week 4	Week 5	Week 8	Week 9	Month 3/ Week 12	Month 5/ Week 20	Month 8/ Week 32	Month 12/ Week 48
Consent	X									
Clinical Exam	X						X	X	X	X
Labs	X							X*		X
Phototrichograms & Macroscopic Photos	X						X	X	X	X
Questionnaire	X						X	X	X	X
PRP Injections	X		X		X					
Minoxidil Treatment Daily								X		
Adverse Events		X	X	X	X	X	X	X	X	X
Clinical Assessment of Injection Sites		X		X		X				
Collection of Research Samples	X		X		X					

*- pre-menopausal patients will have a second pregnancy test at the end of the washout period before beginning the cross-over treatment.

Arm B – MNX then PRP

Procedure	Baseline	Month 3/ Week 12	Month 5/ Week 20	Week 21	Week 24	Week 25	Week 28	Week 29	Month 8/ Week 32	Month 12/ Week 48
Consent	X									
Clinical Exam	X	X	X						X	X
Labs	X		X*							X
Phototrichograms & Macroscopic Photos	X	X	X						X	X
PRP Injections			X		X		X			
Minoxidil Treatment Daily	X									
Questionnaire	X	X	X						X	X
Adverse Events		X	X	X	X	X	X	X	X	X
Clinical Assessment of Injection Sites				X		X		X		
Collection of Research Samples			X		X		X			

*- pre-menopausal patients will have a second pregnancy test at the end of the washout period before beginning the cross-over treatment.

7 Statistical Plan

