For this study, the study treatment follow-up period is 12 months after enrollment. The adverse event monitoring period will end at the end of the follow-up period. If an event is reported after this time it would not be considered study related.

Preexisting Condition

A preexisting condition is one that is present at the start of the study. A preexisting condition should be recorded as an adverse event if the frequency, intensity, or the character of the condition worsens during the study period.

General Physical Examination Findings

At screening, any clinically significant abnormality should be recorded as a preexisting condition. At the end of the study, any new clinically significant findings/abnormalities that meet the definition of an adverse event must also be recorded and documented as an adverse event.

Post-study Adverse Event

All unresolved adverse events should be followed by the sponsor-investigator until the events are resolved, the subject is lost to follow-up, or the adverse event is otherwise explained. At the last scheduled visit, the sponsor-investigator should instruct each subject to report, to the sponsor-investigator, any subsequent event(s) that the subject, or the subject's personal physician, believes might reasonably be related to participation in this study.

Abnormal Laboratory Values

A clinical laboratory abnormality should be documented as an adverse event if it was exhibited as a severe reaction i.e. swelling, that required hospitalization or additional clinical intervention.

Hospitalization, Prolonged Hospitalization or Surgery

Any adverse event that results in hospitalization or prolonged hospitalization should be documented and reported as a serious adverse event unless specifically instructed otherwise in this protocol. Any condition responsible for surgery should be documented as an adverse event if the condition meets the criteria for an adverse event.

Neither the condition, hospitalization, prolonged hospitalization, nor surgery are reported as an adverse event in the following circumstances:

- Hospitalization or prolonged hospitalization for diagnostic or elective surgical procedures for a preexisting condition. Surgery should **not** be reported as an outcome of an adverse event if the purpose of the surgery was elective or diagnostic and the outcome was uneventful.
- Hospitalization or prolonged hospitalization required to allow efficacy measurement for the study.

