8.5 Medical Monitoring

It is the responsibility of the Principal Investigator to oversee the safety of the study at his/her site. This safety monitoring will include careful assessment and appropriate reporting of adverse events as noted above, as well as the construction and implementation of a site data and safety-monitoring plan (see section 10 “Study Monitoring, Auditing, and Inspecting”). Medical monitoring will include a regular assessment of the number and type of serious adverse events.

9 Data Handling and Record Keeping

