10.1 Study Monitoring Plan

The investigator will allocate adequate time for such monitoring activities. The Investigator will also ensure that the monitor or other compliance or quality assurance reviewer is given access to all the study-related documents and study related facilities (e.g. pharmacy, diagnostic laboratory, etc.), and has adequate space to conduct the monitoring visit.

The study specific DSMP will be submitted to the IRB as a separate document in the IRB application.

This study will be monitored on a routine basis during the conduct of the trial. The Mayo Clinic Office of Research Regulatory Support will assist in coordination of the clinical monitoring for the trial as a service for the sponsor-investigator. Clinical trial monitoring requires review of the study data generated throughout the duration of the study to ensure the validity and integrity of the data along with the protection of human research subjects. This will assist sponsor-investigators in complying with Food and Drug Administration regulations.

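### The only mandatory SAE pause in the protocol (Section 8.4) needs three affected subjects in a row, so three to five scattered SAEs among 23 subjects would rarely trigger it

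*Combined protocol and SAP*

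**What the plan says.** Section 8.4 (Stopping Rules) suspends enrollment and treatment if "3 successive subjects experience a Serious Adverse Event within the first 3 months after treatment". The study resumes after a review of the incidents, corrective steps and consultation with the IRB. The section does not say which ordering makes subjects successive, or when the three months start.

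Other safety provisions in the protocol:

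- Section 8.5: "Medical monitoring will include a regular assessment of the number and type of serious adverse events". It sets no threshold and attaches no action to that review. It also makes the investigator responsible for building and running a site safety-monitoring plan.
- Section 10.1: "The study specific DSMP will be submitted to the IRB as a separate document in the IRB application". That plan is not part of the document reviewed here.
- Sections 8.2 and 8.3: recording, protective action for the participant concerned, and reporting to the IRB and FDA.
- Section 4.4.1: withdrawal of individual subjects.
- Section 7.2: no interim analysis.

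Section 7.1 sets the sample at 23. Section 1.4 expects few problems: "Published human data indicate no significant adverse events related to injection of PRP into the skin".

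**The concern.** A rule based on a run needs at least three affected subjects, but three are not enough: they must also be neighbours in the sequence. In a small pilot with a low expected SAE rate, a real safety signal is more likely to be a handful of scattered events than three in a row. In that case 8.4 requires nothing, and a pause rests on discretion. This matters here because Section 3.2 makes morbidity from PRP a primary endpoint and the primary hypothesis in Section 7.2 is that PRP is safe.

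Two terms also leave room for different readings.

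- **Successive.** This could mean enrollment order, treatment order or order within an arm.
- **After treatment.** Section 5.2 describes PRP as given "every 4 weeks for a total of 3 treatments over 12 weeks", so the clock could start at each injection or at the end of the course. In a crossover it could also apply to either period.

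Two members of staff could therefore apply 8.4 differently to the same events.

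**Working it through.** The protocol gives no operating characteristics for the rule and no SAE rate, so there is no stated figure to reproduce.

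**1. Probability of a trigger for a given number affected.** Inputs: n = 23 (Section 7.1) and a run of 3 (Section 8.4). Assumption: one ordered sequence, with all C(23, k) placements of k affected subjects equally likely. No SAE rate is needed.

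- k = 3: there are 21 blocks of three neighbours. 21 / C(23,3) = 21/1771 = 1.2%.
- k = 4: 21 blocks × 20 places for the fourth subject = 420. The 20 runs of four are each counted twice, so 420 − 20 = 400. 400/8855 = 4.5%.
- k = 5: 19 runs of five. Runs of exactly four plus one: 2×18 + 18×17 = 342. Runs of exactly three plus two: 2×C(19,2) + 19×C(18,2) = 342 + 2907 = 3249. Total 19 + 342 + 3249 = 3610. 3610/33649 = 10.7%.

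**2. When the trigger becomes certain.** With 16 affected, the 7 unaffected subjects leave 8 gaps, and two affected subjects in each gap make 16 with no run of three. With 17 affected, 6 unaffected leave 7 gaps, which hold at most 14 without a run. So 17 is the first number that guarantees a trigger. This is a bound, not a scenario to expect.

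**3. The same scale for a count of 3.** A pooled count over both treatments pauses with certainty at 3. With separate tallies for PRP and minoxidil, suppose each affected subject has an SAE on one treatment, either with equal chance:

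- 3 affected: all on one treatment, 2/8 = 25%.
- 4 affected: every split except 2+2, 1 − 6/16 = 62.5%.
- 5 affected: one treatment must have at least 3, so 100%.

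**4. Chance of a pause at assumed SAE rates.** Assume rate p on each treatment, with subjects and treatments independent. For threshold c, one tally pauses with T = P(Bin(23, p) ≥ c), and either tally with 1 − (1 − T)². For the current rule and a pooled count, a subject is affected on either treatment with q = 1 − (1 − p)², which is 3.96% at p = 2% and 9.75% at p = 5%.

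| Rule | p = 2% | p = 5% |
|---|---|---|
| Current run of 3 | 0.1% | 1.8% |
| Separate tallies, threshold 3 (T = 1.05%, 10.52%) | 2.1% | 19.9% |
| Separate tallies, threshold 4 (T = 0.10%, 2.58%) | 0.2% | 5.1% |
| Pooled count of 3 | 6.1% | 39.2% |

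**5. Windows under the proposed count.** These come from Section 6.1, "PRP vs Minoxidil Study Calendars", with 3 months taken as 12 weeks and each window running from first dose to 12 weeks after last dose.

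- Arm A: PRP at weeks 0, 4 and 8, closing at about week 20. Minoxidil weeks 20 to 32, closing at about week 44.
- Arm B: minoxidil weeks 0 to 12, closing at about week 24. PRP at weeks 20, 24 and 28, closing at about week 40.

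The Arm B windows overlap in weeks 20 to 24, because minoxidil is "followed by a two month (8 week) washout period" and 8 weeks is shorter than 12. All windows close before the week 48 visit.

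**The case against.** **The probabilities depend on one reading.** They need a single sequence and equally likely orders. If the word successive meant SAEs following one another in calendar time, 8.4 would already be a count rule. This stands as a limit on the figures. It does not remove the point, because the ordinary sense of successive subjects is a run, and wording that allows both readings needs redrafting anyway.

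**The required pause may exist elsewhere.** The monitoring plan may hold a count rule, and then the defect is only a missing cross-reference. This stands in full. A reader might infer that several SAEs could pass without any response, or that the trial has no effective safety brake. The documents do not support that: investigator evaluation, protective action, regular SAE review and IRB and FDA reporting are all required, and any of them may lead to a pause. What the protocol lacks is a mandatory pause that responds to the number affected.

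**Large numbers of affected subjects are implausible.** On the rates assumed above, 5 or more affected has probability 0.2% (p = 2%) or 6.7% (p = 5%). The argument should therefore rest on 3 to 5 affected. A reader might also infer that number is irrelevant to the current rule. It is not: at least 3 are needed, and the probability rises with each additional one.

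**The replacement is not free or complete.** Separate tallies can also miss 3 or 4 affected subjects (step 3). At 5% they raise the chance of a pause from 1.8% to 19.9%, counting SAEs whether or not they are related to treatment. The comparison may not be like for like: the proposed window is about 20 weeks for PRP and 24 for minoxidil, against about 12 if the current wording means after the course. All of this stands and belongs in the decision.

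**Conclusion.** The point holds for the mandatory trigger in 8.4. On its plain reading, with all orders equally likely, the rule would stay silent about 99%, 95% and 89% of the time when 3, 4 and 5 of 23 subjects have an SAE. In a population screened for significant disease, with few events expected, that many would be a signal worth a pause. The percentages illustrate one reading of an undefined term, and the pause rates rest on assumed SAE rates. Whether a gap remains once the monitoring plan is read cannot be settled from the protocol. The change is worth making because it concerns participant protection, needs little text, and leads to a pause that 8.4 already treats as reversible.

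**What to change.** In 8.4, replace the run of three with a cumulative count. Suggested wording for the condition: *3 or more subjects, in any order, have had a Serious Adverse Event from the first dose of a treatment until 3 months after its last dose, counted separately for PRP and MNX; an event that falls in both windows is assigned to the most recent treatment.* The last clause deals with the Arm B overlap. This wording also settles both undefined terms. If the monitoring plan already has a count rule, refer to it in 8.4 instead.

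The sponsor and IRB should choose the number and the form of the count knowing the trade-off:

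- Separate tallies of 3 guarantee a pause only from 5 affected subjects (25% at 3 and 62.5% at 4 under the equal-chance assumption).
- A pooled count of 3 always pauses at 3, but pauses more often at the assumed background rates (6.1% and 39.2%).
- Separate tallies of 4 keep unnecessary pauses low (0.2% and 5.1%), but cannot pause at 3 and guarantee a pause only from 7 affected, since 6 can split 3+3.

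The cost is a short change to 8.4, more temporary pauses, and a counting window that may be wider than the present one. No new visits or data are needed: the windows close by about week 44, and on the 12-month follow-up in Section 8.1, "The adverse event monitoring period will end at the end of the follow-up period".

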8.5 Medical Monitoring

It is the responsibility of the Principal Investigator to oversee the safety of the study at his/her site. This safety monitoring will include careful assessment and appropriate reporting of adverse events as noted above, as well as the construction and implementation of a site data and safety-monitoring plan (see section 10 “Study Monitoring, Auditing, and Inspecting”). Medical monitoring will include a regular assessment of the number and type of serious adverse events.

9 Data Handling and Record Keeping

9.1 Data Handling

Data will be collected and entered by the study coordinator assigned to the project, and stored into a REDCap database.

9.2 Confidentiality

Information about study subjects will be kept confidential and managed according to the requirements of the Health Insurance Portability and Accountability Act of 1996 (HIPAA). Those regulations require a signed subject authorization informing the subject of the following:

- What protected health information (PHI) will be collected from subjects in this study
- Who will have access to that information and why
- Who will use or disclose that information
- The rights of a research subject to revoke their authorization for use of their PHI.

In the event that a subject revokes authorization to collect or use PHI, the investigator, by regulation, retains the ability to use all information collected prior to the revocation of subject authorization. For subjects that have revoked authorization to collect or use PHI, attempts should be made to obtain permission to collect at least vital status (long term survival status that the subject is alive) at the end of their scheduled study period.

Hard copy data such as consent forms will be stored in locked file cabinets; electronic data will be stored in secure web-based database (REDCap) that will be designed with the help of the statistician.

9.3 Source Documents

Source data are all information, original records of clinical findings, observations, or other activities in a clinical trial necessary for the reconstruction and evaluation of the trial. Source data are contained in source documents. Examples of these original documents, and data records include: hospital records, clinical and office charts, laboratory notes, memoranda, subjects' diaries or evaluation checklists, pharmacy dispensing records, recorded data from automated instruments, copies or transcriptions certified after verification as being accurate and complete, microfiches, photographic negatives, microfilm or magnetic media, x-rays, subject files, and records kept at the pharmacy, at the laboratories, and at medico-technical departments involved in the clinical trial.

Data Management

Study data will be managed in a study specific REDCap system

Data Security and Confidentiality

The REDCap system has built in systems for control of access, data integrity and audit trails. Access and confidentiality are controlled in a manner similar to other institutional systems.

9.4 Records Retention

The sponsor-investigator will maintain records and essential documents related to the conduct of the study. These will include subject case histories and regulatory documents.

The sponsor-investigator will retain the specified records and reports for whichever is longer;

1. Up to 2 years after the marketing application is approved for the drug; or, if a marketing application is not submitted or approved for the drug, until 2 years after shipment and delivery of the drug for investigational use is discontinued and the FDA has been so notified. OR
2. As outlined in the Mayo Clinic Research Policy Manual "Access to and Retention of Research Data Policy" http://mayocontent.mayo.edu/research-policy/MSS_669717.

10 Study Monitoring, Auditing, and Inspecting

10.1 Study Monitoring Plan

The investigator will allocate adequate time for such monitoring activities. The Investigator will also ensure that the monitor or other compliance or quality assurance reviewer is given access to all the study-related documents and study related facilities (e.g. pharmacy, diagnostic laboratory, etc.), and has adequate space to conduct the monitoring visit.

The study specific DSMP will be submitted to the IRB as a separate document in the IRB application.

This study will be monitored on a routine basis during the conduct of the trial. The Mayo Clinic Office of Research Regulatory Support will assist in coordination of the clinical monitoring for the trial as a service for the sponsor-investigator. Clinical trial monitoring requires review of the study data generated throughout the duration of the study to ensure the validity and integrity of the data along with the protection of human research subjects. This will assist sponsor-investigators in complying with Food and Drug Administration regulations.

10.2 Auditing and Inspecting

The investigator will permit study-related monitoring, audits, and inspections by the IRB, the sponsor, and government regulatory agencies, of all study related documents (e.g. source documents, regulatory documents, data collection instruments, study data etc.). The investigator will ensure the capability for inspections of applicable study-related facilities (e.g. pharmacy, diagnostic laboratory, etc.).

Participation as an investigator in this study implies acceptance of potential inspection by government regulatory authorities and applicable compliance offices.

11 Ethical Considerations

This study is to be conducted according to United States government regulations and Institutional research policies and procedures.

This protocol and any amendments will be submitted to a properly constituted local Institutional Review Board (IRB), in agreement with local legal prescriptions, for formal approval of the study. The decision of the IRB concerning the conduct of the study will be made in writing to the sponsor-investigator before commencement of this study.

All subjects for this study will be provided a consent form describing this study and providing sufficient information for subjects to make an informed decision about their participation in this study. This consent form will be submitted with the protocol for review and approval by the IRB for the study. The formal consent of a subject, using the Approved IRB consent form, must be obtained before that subject undergoes any study procedure. The consent form must be signed by the subject or the subject's legally authorized representative, and the individual obtaining the informed consent.

12 Study Finances

